## **6.0 Analysis Conventions**

### **6.1 Definition of Baseline and Final Observation**

Baseline of the parent study, Study M10-877/M10-880, is defined as the last non-missing observation made on or prior to the first dose of study drug in Study M10-877/M10-880.

Baseline of Study M11-327 is defined as the last non-missing observation made on or prior to the first dose of study drug in Study M11-327.

The final observation is defined as the last non-missing observation available prior to last dose plus 70 days.

### **6.2 Definition of Rx Days and Visit Windows**

Rx Days for efficacy analyses are calculated for each time point relative to the first adalimumab dose date in Study M11-327. Rx days are negative values when the time point of interest is prior to the first adalimumab dose day. Rx days are positive values when the time point of interest is after the first adalimumab dose day. The day of the first dose of adalimumab is defined as Rx Day 1, while the day prior to the first adalimumab dose is defined as Rx Day –1 (there is no Rx Day 0). Rx Days are calculated as:

## Rx Day

- = Date of the measurement – Day 1 + 1 if date of measurement  $\geq$  Day 1 date, or
- = Date of the measurement – Day 1 if date of measurement  $<$  Day 1 date.

All time points and corresponding time windows for efficacy analyses are defined based on Rx Days for efficacy analyses. If more than one assessment is included in a time window the assessment closest to the nominal day should be used. If there were two observations equally distant to the nominal day, the latest one will be used in analyses. If more than one assessment is included on the same day, then the last assessment on that day will be used in analyses.

The following visit windows will be used for efficacy analyses:

Visit Windows			
Week	Nominal Rx Day	First Rx Day	Last Rx Day
0	1	-	1
2	15	2	22
4	29	23	43
8	57	44	71
12	85	72	106
18	127	107	169
$18+i*12^a$	$127+i*84$	$170+(i-1)*84$	$169+i*84$

a     i = 1, 2, 3, 4 etc.

Rx Days for safety analyses are calculated for each time point relative to the first adalimumab dose date in Study M10-877, M10-880 or M11-327. Rx days are negative values when the time point of interest is prior to the first adalimumab dose day. Rx days are positive values when the time point of interest is after the first adalimumab dose day. The day of the first dose of adalimumab is defined as Rx Day 1, while the day prior to the first adalimumab dose is defined as Rx Day –1 (there is no Rx Day 0).

## **6.3 Imputation of Missing Data**

The following imputation methods will be used to impute missing values in the efficacy analyses. In addition, an observed case analysis will be performed.

- Non-Responder Imputation (NRI)
- Last Observation Carried Forward (LOCF)

In case of an interim analysis, NRI and LOCF will be used. Values will be imputed until that visit that the subject could have reached based on the cutoff date.

### **6.3.1 Non-Responder Imputation (NRI)**

The NRI approach is used for binary variables. These variables can take values of 'Response' or 'Non-Response' or can be missing for any reason including discontinuation from study. According to the NRI imputation approach, all missing values will be considered as non-response.

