5.2.3.2 Concomitant Therapy

All medications (including, but not limited to, prescription or over-the-counter medicines such as aspirin, antacids, vitamins, mineral supplements, and herbal preparations) that the subject is receiving from Baseline through the end of the study, must be recorded on the appropriate electronic Case Report Form (eCRF) along with the reason for use, dates of administration including start and end dates, and dosage including dose, frequency and route of administration.

Subjects will be allowed two periocular corticosteroid injections per eye per year during the duration of the study at the investigator's discretion. No intraocular or intravitreal injections will be allowed.

Subjects will be allowed to continue on one ongoing non-biologic protocol-permitted immunosuppressive therapy and one systemic corticosteroid at study entry. Alternatively, if the subject has not been on a non-biologic immunosuppressive previously, they can add one of the following at any time during the Study M11-327. In addition, doses must be within the acceptable limits listed below:

- Methotrexate (MTX) \leq 25 mg per week

- Cyclosporine \leq 4 mg/kg per day
- Mycophenolate mofetil \leq 2 grams per day or an equivalent drug to mycophenolate mofetil (e.g., mycophenolic acid) at an equivalent dose approved by the Medical Monitor
- Azathioprine \leq 175 mg per day
- Tacrolimus (oral formulation) \leq 8 mg per day

The non-biologic immunosuppressive drug and/or corticosteroids can be initiated, changed or discontinued during the course of the study if it is considered appropriate for the subject in the investigator's expert opinion.

Dosage of topical eye drops (including topical corticosteroid eye drops) may be initiated or adjusted as medically necessary during the study.

The initiation, discontinuation and/or changes in dosing of these non-biologic immunosuppressive therapies and corticosteroids can have an impact on uveitis. However, the intent of allowing these to occur, is to reflect standard clinical practice in the management of uveitis.

Each vaccine administered to the subject should be listed as a concomitant medication on the Other Medications eCRF. Live vaccines may not be given concurrently while on study drug or for 70 days after the last dose of adalimumab.

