5.2.3.3 Prohibited Therapy

With the exception of one allowed concomitant immunosuppressant, systemic/topical/periorcular (per eye) corticosteroids as detailed in Section 5.2.3.2, the introduction of other medications for uveitis is prohibited during the study.

The following medications are prohibited during the study:

- All biologic therapies with a potential therapeutic impact on non-infectious uveitis, including but not limited to the following:
 - Enbrel[®] (etanercept);

- Remicade[®] (infliximab);
- Simponi[®] (golimumab);
- Orencia[®] (abatacept);
- Kineret[®] (anakinra);
- Rituxan[®]/MabThera[®] (rituximab);
- Tysabri[®] (natalizumab);
- Actemra[®]/RoActemra[®] (tocilizumab);
- Raptiva[®] (efalizumab);
- Cimzia[®] (certolizumab pegol);
- Stelara[®] (ustekinumab);
- Benlysta[®] (belimumab);
- Anti-VEGF therapy
- Live vaccines (during the study and for 70 days after the last dose of study drug) (including but not limited to the following: monovalent live attenuated influenza A (H1N1) [intranasal], seasonal trivalent live attenuated influenza (intranasal), herpes zoster, rotavirus, varicella (chicken pox), measles-mumps-rubella (MMR) or MMRV (measles-mumps-rubella-varicella), oral polio vaccine (OPV), smallpox, yellow fever, Bacillus Calmette-Guerin (BCG) and typhoid
- Rifampin/Pyrazinamide combination
- Anti-retroviral therapy
- All other immunosuppressive therapy other than MTX, cyclosporine, mycophenolate mofetil or an equivalent drug to mycophenolate mofetil (e.g., mycophenolic acid), azathioprine, and tacrolimus (oral formulation)
- Intraocular or intravitreal corticosteroid injections
- Ozurdex[®] (dexamethasone implant)
- Intravitreal MTX
- Medical or recreational marijuana
- Systemic carbonic anhydrase inhibitor

- Any TB-prophylaxis therapy (except for those subjects who entered the parent study prior to Study M10-877 Amendment 6 or Study M10-880 Amendment 7 and were still taking TB-prophylaxis when they entered Study M11-327)
- Retisert[®] (glucocorticosteroid implant)
- Cyclophosphamide
- Chlorambucil

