5.4 Removal of Subjects from Therapy or Assessment

5.4.1 Discontinuation of Individual Subjects

A subject may withdraw from the study at any time. The Investigator may discontinue any subject's participation for any reason, including an adverse event, safety concerns or failure to comply with the protocol. Please refer to Section 6.3, Toxicity Management, for more information regarding the type and duration of follow-up of subjects after adverse events.

Subjects will be withdrawn from the study immediately if any one of the following occurs:

- Clinically significant abnormal laboratory result(s) or adverse event(s), as determined by the Investigator in consultation with the AbbVie Medical Monitor.
- The Investigator believes it is in the best interest of the subject.
- The subject requests withdrawal from the study.
- Inclusion and exclusion criteria violation was noted after the subject started study drug, when continuation of the study drug would place the subject at risk as determined by the AbbVie Medical Monitor.
- Introduction of prohibited medications or dosages when continuation of the study drug would place the subject at risk as determined by the AbbVie Medical Monitor.
- Subject has positive PPD test or positive (or indeterminate re-test) QuantiFERON[®]-TB Gold test (or IGRA equivalent) result at Baseline, Week 42, 90, 138, 186, 234, 282, or 330.
- Subject is non-compliant with TB prophylaxis (for those subjects who entered the parent study prior to Study M10-877 Amendment 6 or Study M10-880 Amendment 7 and were still taking TB Prophylaxis when they entered Study M11-327).
- Subject becomes pregnant while on study medication.
- Subject has known dysplasia of the gastrointestinal tract (a colonoscopy is not required to enter the study) or a malignancy, except for localized non-melanoma skin cancer. Discontinuation for carcinoma in-situ of the cervix is at the discretion of the Investigator.
- Subject is diagnosed with lupus-like syndrome, multiple sclerosis or demyelinating disease.
- Subject is significantly non-compliant with study procedures which would put the subject at risk for continued participation in the trial as determined by the Investigator, in consultation with the AbbVie Medical Monitor.

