6.3 Toxicity Management

For the purpose of medical management, all adverse events and laboratory abnormalities that occur during the study must be evaluated by the Investigator. Subjects who develop a new infection while receiving study drug should be monitored closely. Administration of study injections should be interrupted if a subject develops an infection requiring IV anti-infective treatment or if an infection meets the definition of "serious" (refer to Section 6.1.1.2 for definitions). Study medication may be restarted once the physician determines that the infection has been successfully treated. Otherwise prohibited concomitant medications may be given if medically necessary. Prior to use, every attempt

should be made to contact the AbbVie Study Physician for direction on re-introduction of study drug after prohibited medication administration.

If the subject must undergo elective surgery, the study injections must be interrupted 2 weeks prior to the surgery. If the subject must undergo emergency surgery, the study injections must be interrupted at the time of the surgery. The injectable study medication can recommence at least 2 weeks after surgery once the physician has examined the surgical site and determined that it has healed and there is no sign of infection.

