## **7.5 Concomitant Medications**

Medications with a start date prior to or on the first dose of adalimumab in Study M11-327 and a stop date on or after the first dose of adalimumab in Study M11-327 or a missing stop date will be considered as concomitant medications at baseline of Study M11-327. If the start date is missing and the stop date is on or after the baseline date in Study M11-327, or if start and stop dates are both missing, the medication will also be considered as concomitant at baseline in Study M11-327. The following therapies used by subjects at baseline in Study M11-327 will be summarized by counts and percentages:

- Immunosuppressants (IMMs)
  - Azathioprine

- Cyclosporine
- Methotrexate (MTX)
- Mycophenolate mofetil or equivalent drug (e.g. mycophenolic acid)
- Tacrolimus
- Corticosteroids (CSs)
  - Oral corticosteroids
  - Topical corticosteroids
  - Other corticosteroids

Concomitant medication is defined as any medication that started prior to the first dose of adalimumab in Study M11-327 and continued to be taken after the first dose of adalimumab in Study M11-327 or any medication that started after the first dose of adalimumab in Study M11-327, but not after the last dose of adalimumab in Study M11-327. The number and percentage of subjects who had taken concomitant medications will be summarized by generic drug name based on the World Health Organization (WHO) drug dictionary.

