### **10.2 Efficacy Variables**

The following efficacy variables will be analyzed:

- Proportion of subjects with no active lesions in both eyes at each study time point.
- Proportion of subjects at each study time point with no new active, inflammatory chorioretinal or inflammatory retinal vascular lesion in both eyes relative to Baseline for subjects who had inactive uveitis when they entered the study and to Week 8 for subjects who had active uveitis when they entered the study.
- AC cell grade left/right eye and mean of both eyes at each study time point.
- Proportion of subjects at each study time point with a Grade  $\leq 0.5+$  in AC cells in both eyes on Slit Lamp Exam, according to SUN criteria.

- VH grades left/right eye and mean of both eyes at each study time point.
- Proportion of subjects at each study time point with a Grade  $\leq 0.5+$  in vitreous haze in both eyes on indirect ophthalmoscopy, according to NEI/SUN criteria.
- Proportion of subjects at each study time point with VH  $\leq 0.5$  and AC  $\leq 0.5$ .
- Proportion of subjects at each study time point with new lesions, AC  $\geq 2$  or VH  $\geq 2$ .
- Proportion of subjects at each study time point in quiescence defined as no active lesions, AC  $\leq 0.5$  and VH  $\leq 0.5$ .
- Proportion of subjects who experienced a uveitis flare (defined as no quiescence) during the study and who did or did not discontinue from the study due to the flare.
- LogMAR Best corrected visual acuity (BCVA) left/right eye and mean of both eyes at each study time point.
- Proportion of subjects at each study time point without a worsening of BCVA by  $\geq 15$  letters on the Early Treatment Diabetic Retinopathy Study (ETDRS) in both eyes relative to Baseline for subjects who had inactive uveitis when they entered the study and to Week 8 for subjects who had active uveitis when they entered the study.
- Proportion of subjects who started IMMs in Study M11-327.
- Proportion of subjects on/off IMMs at each study time point only in subjects on IMMs at baseline of Study M11-327.
- Proportion of subjects at each study time point achieving a  $\geq 50\%$  reduction in immunosuppression load relative to Baseline for subjects who had inactive uveitis when they entered the study and to Week 8 for subjects who had active uveitis when they entered the study.

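### NRI in SAP 6.3.1 fails only missing values, so a subject kept on study after a prohibited uveitis drug can score as a responder while one withdrawn after the same drug cannot (minor, cheap to fix)

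*SAP*

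**What the plan says.** SAP 6.3.1 gives NRI a single trigger: "all missing values will be considered as non-response", whatever the reason for missingness, discontinuation included. SAP 10.2 applies NRI to the categorical efficacy variables, alongside an as-observed analysis. The central variable, the proportion "in quiescence defined as no active lesions" plus low anterior chamber cell and vitreous haze grades, carries no condition on medication.

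Protocol 5.2.3.3 allows one immunosuppressant and certain corticosteroids and otherwise states that "the introduction of other medications for uveitis is prohibited during the study". Its list includes other biologics, anti-VEGF, intraocular or intravitreal steroid, steroid implants, intravitreal methotrexate, cyclophosphamide and chlorambucil.

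Withdrawal after such a drug is conditional. Among the triggers in Protocol 5.4.1 is "Introduction of prohibited medications or dosages when continuation of the study drug would place the subject at risk", with the risk judged by the sponsor's medical monitor. Protocol 6.3 adds "Otherwise prohibited concomitant medications may be given if medically necessary" and says that every attempt "should be made to contact the AbbVie Study Physician for direction on re-introduction of study drug after prohibited medication administration". Staying on study after a prohibited drug is therefore foreseen.

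**The concern.** NRI is normally read as the conservative analysis, in which leaving treatment counts as failure. Here the score after a prohibited uveitis drug depends on the retention decision. If the subject is withdrawn, later visits are missing and fail. If the subject is kept, the eye examination is present and is scored as seen, although the quiet eye may be due to the prohibited drug. Two subjects with the same drug and the same eyes can get opposite scores.

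At stake is the level of the long-term NRI proportions (lesions, cells, haze, quiescence, steroid-free quiescence, visual acuity worsening, macular edema), which can be a little too favourable. The primary safety objective is not affected.

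**Working it through.** The plan states no power, alpha or computed sample size, so there is no design figure to reproduce. The check has a textual part and a sizing part.

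**Is there a rule elsewhere?**
- SAP 5.1 removes subjects from the ITT set for on-study cataract surgery, vitrectomy or diabetic eye disease, and at two investigators. Prohibited therapy is not among the reasons.
- SAP 6.3.3 (observed case) drops missing values only. It keeps the retained subject's quiet visits and loses the withdrawn subject's later ones.
- Protocol 8.1.1 rules out a per-protocol analysis.
- Protocol 7.0 makes prohibited treatment a reportable deviation and SAP 8.0 counts deviations. Neither changes a score.
- SAP 10.1, 10.2 and 10.4 contain no rule for values seen after prohibited therapy.

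**Size per subject.** N is about 400 (Protocol 5.2); stratum sizes are assumed.
- All subjects: 1/400 = 0.25 points per retained quiet subject at a visit; 4/400 = 1 point.
- Assumed strata of 300 and 100 (active or inactive at entry): 1/300 = 0.33 and 1/100 = 1.0 points.

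**Against sampling error.** The 95% half-width is 1.96 × √(p(1−p)/400).
- p = 0.8 (assumed): 1.96 × √(0.16/400) = 3.9 points, or 0.0392 × 400 = 15.7 subjects.
- p = 0.5 (assumed): 1.96 × √(0.25/400) = 4.9 points, or 0.049 × 400 = 19.6 subjects.

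About 16 to 20 retained quiet subjects at one visit would be needed to move the estimate by a half-width.

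**Dependence on the retention decision.** Let x be the share of subjects given a prohibited uveitis-active drug and q the share of those who are quiet at a later visit. The documents give neither. The difference between keeping all and withdrawing all is x × q.
- x = 1%, q = 50% to 100%: 0.5 to 1.0 points.
- x = 3%: 1.5 to 3.0 points.
- x = 5%: 2.5 to 5.0 points.
- x = 10%: 5.0 to 10.0 points, shown only to bound the scale.

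For example, with 20 exposed of 400 and q = 0.8, NRI counts 0 responders if all are withdrawn, 10 × 0.8 = 8 if half are kept and 20 × 0.8 = 16 if all are kept. The range is 16/400 = 4.0 points. If every visit from the first dose onward is scored as non-response, the count is 0 in all three cases and the dependence disappears.

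**Visits touched.** Visits are every 12 weeks after Week 18. For a drug started just after Week 30 (assumed), the visits from Week 42 to Week 330, the last visit named for TB testing, number (330 − 42)/12 + 1 = 25. This counts visits up to Week 330 for a subject who stays that long; local approval ends participation earlier for many (Protocol 5.1).

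**Early Termination visit.** A withdrawn subject may have one quiet examination after the drug. Protocol 5.4.1 wants that visit within 2 weeks of the last dose and preferably before new therapy, so at most one window is involved.

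**The case against.** **The route is narrow.** This is largely right. The permission in Protocol 6.3 sits in general toxicity management, next to infections and surgery. A reader might take it as a rescue route for uveitis, but the text does not say so. Flares have their own rule in Protocol 5.1: an active flare lasting 4 weeks or more should end participation. Protocol 5.2.3.2 leaves wide permitted options, and Protocol 7.0 does not allow intentional deviations. What remains is a flare quickly suppressed by a prohibited drug in a subject not judged at risk. It does not meet the 4-week rule, and with visits 12 weeks apart SAP 6.2 uses the examination nearest the nominal day.

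**Scoring an observed quiet eye as quiet is a legitimate treatment-policy summary.** It is, and the as-observed analysis keeps it. NRI, however, already counts withdrawal as failure. Counting the same drug as success or failure according to retention follows neither strategy consistently.

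**The use is visible.** Under SAP 7.5, "subjects who had taken concomitant medications will be summarized by generic drug name". SAP 10.2 has an any-flare variable and classifies non-quiescent subjects by change in corticosteroids or immunosuppressants. Its immunosuppression-load table grades cyclophosphamide and chlorambucil. A reader could judge whether the issue matters, but none of these outputs changes a visit's score.

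**Stronger readings that the documents do not support.**
- A reader might want permitted steroid or immunosuppressant changes to count as failure too. Protocol 5.2.3.2 says that "the intent of allowing these to occur, is to reflect standard clinical practice in the management of uveitis", so they belong to the regimen under study.
- A reader might take a response rate from the open-label infliximab study in Protocol 3.5.2 (24 of 31 at Week 10). That endpoint is a composite, not quiescence, and only 15 of the 31 both met it and completed a year. It does not size this bias.

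**Conclusion.** The asymmetry is real and nothing else in the plan removes it. It is a minor point: a small upward bias, probably infrequent, in descriptive, non-primary proportions. The firm figure is 0.25 points per retained quiet subject at N = 400. Any total rests on assumed values of x and q, because the documents give no frequency of prohibited use. A reader might infer that the long-term efficacy results are materially inflated. The documents do not support that: a shift as large as the confidence half-width needs about 16 to 20 such subjects at one visit, and the protocol's safeguards work against such numbers. No hypothesis test or decision rule is involved.

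**What to change.** Before database lock, add one sentence to SAP 6.3.1: in the NRI analysis of the binary disease-activity and visual outcomes, all visits on or after the first dose of a prohibited uveitis-active therapy are scored as non-response (for outcomes worded adversely, as the unfavourable state). Take the therapies from Protocol 5.2.3.3: other biologics, non-permitted immunosuppressants, intraocular or intravitreal steroid or methotrexate, steroid implants, and anti-VEGF. Prohibited drugs without a uveitis effect, such as anti-retrovirals, stay outside the rule.

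Use no duration-of-effect limit for local therapy. An assumed 12 to 24 weeks would cover only 1 to 2 of the 25 visits counted above. The roughly 30 months that Protocol 3.4 gives for the fluocinolone implant (about 130 weeks, Weeks 42 to 150) would cover 10. The asymmetry would return afterwards, and each duration would need clinical debate.

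Leave permitted therapy, the medication-use variables (immunosuppressants started, on or off; steroid dose categories; immunosuppression load) and the as-observed analysis unchanged.

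The cost is one sentence, a short drug list, and programming from drug names, routes and dates that Protocol 5.2.3.2 already requires. NRI proportions will be slightly lower, and a one-off local injection will count as failure from then on. The as-observed analysis still shows the actual values.
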